## **5.8      Duration of Therapy**

If at any time the constraints of this protocol are considered to be detrimental to the patient's health and/or the patient no longer wishes to continue protocol therapy, the protocol therapy will be discontinued and the reason(s) for discontinuation documented in the case report forms.

In the absence of treatment delays due to adverse events, treatment may continue for up to 4 doses of rhIL-7-hyFc or until one of the following criteria applies:

- Documented and confirmed disease progression
- Death
- Adverse event(s) that, in the judgment of the investigator, may cause severe or permanent harm or that rule out continuation of study drug
- General or specific changes in the patient's condition render the patient unable to receive further treatment in the judgment of the investigator
- Confirmed pregnancy
- Serious non-compliance with the study protocol
- Lost to follow-up
- Patient withdraws consent
- Investigator removes the patient from study
- The Siteman Cancer Center decides to close the study

Patients who prematurely discontinue treatment for any reason will be followed as indicated in the study calendar.

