### **5.9 Duration of Follow-up**

Patients will only be off study at the time of death. All patients will be assessed for survival by phone call, clinic visit, or medical records (e.g. physician notes/laboratory results of clinic or hospital visit) at 2 years and 5 years following the end of study treatment.

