#### **13.4.6 Progression-Free Survival**

PFS is defined as the duration of time from start of treatment to time of progression or death, whichever occurs first.

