#### **15.3.5 Statistical Analysis**

All data will be analyzed as observed and no imputation for missing values will be used. Patient characteristics will be summarized by descriptive statistics. Descriptive statistics will be used to summarize the trial results, i.e., statistics for continuous variables such as lymphocyte counts may include means, medians, ranges and appropriate measures of variability. Qualitative variables will be summarized by counts and percentages. The uncertainty of estimates will be assessed by confidence intervals (CIs). Markers for lymphocyte recovery in each group will be summarized as means and standard deviations (SD) at each time point. The primary endpoint, ALC at ~ week 4 and the change from the time point of radiation will be compared between the two arms by two sample t-test or Wilcoxon rank sum test as appropriate and by a linear model where other important factors such as concomitant use of steroid besides the treatment arm will be modeled. Within each arm, the primary endpoint will be compared to the ALC at the completion of radiation by paired sample t-test or Wilcoxon signed rank test as proper. Total lymphocyte counts at later cycles will be similarly analyzed but may be compared to a different reference time point. We will analyze ALC over time using linear models for repeated measurement data, followed by post-hoc multiple comparisons for between-group differences at other time points of interest. PFS and overall survival will be analyzed using the Kaplan–Meier method and survival difference will be compared between arms by log rank test. The univariate Cox proportional hazard model will be applied to evaluate ALC at each time point, in continuous scale and dichotomized scale by the cutoff of 1 (determined based on literature), for their prognostic effect on PFS and OS while multivariate Cox model will be applied to account for other covariates. The time varying Cox proportional hazard model will be applied to model the prognostic effect of the longitudinal ALC as a whole, without and with additional covariates.

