#### **15.4.2 Endpoint**

The primary endpoint for the expansion cohort is progression free survival (PFS) defined from date of surgery to date of progression or death due to disease or date of last clinical follow up. The secondary endpoints include AE and OS.

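### The fixed-time Cox models of ALC for PFS do not require patients to be progression-free when the ALC is taken, so a post-progression count can enter as a predictor of that progression

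*Combined protocol and SAP*

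**What the plan says.** Section 15.3.5 plans fixed-time models: "The univariate Cox proportional hazard model will be applied to evaluate ALC at each time point", on a continuous and a dichotomized scale, "for their prognostic effect on PFS and OS while multivariate Cox model will be applied to account for other covariates". It then adds a further model: "The time varying Cox proportional hazard model will be applied to model the prognostic effect of the longitudinal ALC as a whole". It says that data are analyzed as observed. It states no landmark, no delayed entry and no rule for ALC values dated after progression.

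Section 13.4.6 gives the outcome: "PFS is defined as the duration of time from start of treatment to time of progression or death, whichever occurs first".

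Three other places bear on which ALC values will exist:
- Section 5.8 lists "Documented and confirmed disease progression" among the reasons for ending study treatment, and then says: "Patients who prematurely discontinue treatment for any reason will be followed as indicated in the study calendar".
- Section 5.9 says: "Patients will only be off study at the time of death".
- The Section 10.1 calendar has a CBC with ALC at 15 visits from screening to W37 and again at W45. Its footnote 8 adds that weekly standard-of-care CBC results are collected.

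**The concern.** A Cox model of PFS on ALC at W25 makes sense only for patients who have not had the PFS event by W25. Nothing in Section 15.3.5 limits it to them. A patient who progresses at month 3 and has a CBC at W25 would enter with a PFS time of 3 months and a covariate measured more than two months after the event.

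The protocol gives reasons why such a count may differ from a pre-progression count. Progression ends rhIL-7-hyFc, which is given to raise ALC, so a patient in the active arm who progresses before the second or third injection misses it. Section 1.1 names glucocorticoids among the treatments that cause lymphopenia. If ALC falls after progression, patients with early events have low counts because of the event, and the model reports that low ALC predicts progression. The time-varying model is a separate analysis and does not correct the fixed-time fits that would be reported beside it.

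**Working it through.** **Plan's own figure.** The documents state no figure for these Cox models. The phase II sample size in Section 15.3.3 (8 per arm, 1486 vs 850, SD 480, one-sided 5% t-test, 80% power) reproduces at 80.9% from the noncentral t distribution. It is not in dispute.

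**Step 1: how many patients may have progressed before a visit.** With exponential PFS of median m months and W1 as time zero, the share is 1 − 2^(−t/m), where t = (week − 1)/4.345 months. The only medians available for illustration are 6.3 and 11.5 months (Section 15.4.3). For W25, t = 24/4.345 = 5.52, so the share is 1 − 2^(−5.52/6.3) = 46% or 1 − 2^(−5.52/11.5) = 28%.

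| Visit | m = 6.3 | m = 11.5 |
|---|---|---|
| W4 | 7% | 4% |
| W13 | 26% | 15% |
| W25 | 46% | 28% |
| W37 | 60% | 39% |
| W45 | 67% | 46% |

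**Step 2: null simulation.** ALC has no effect on PFS. From the documents: N = 20, ALC mean 850 and SD 480, and the two medians. Assumed: exponential PFS, 104 weeks of follow-up, median survival after progression of 8 months, a CBC for every patient alive at the visit, and an ALC fall after progression of 0, 200 or 400 (0%, 24% or 47% of 850). There were 2,000 runs per setting, so the Monte Carlo standard error is about 0.5 points at 5% and 0.9 points at 20%. The table shows the fixed-time model: HR per SD of higher ALC, with the two-sided 5% rejection rate in brackets.

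| m, visit | Fall 0 | Fall 200 | Fall 400 |
|---|---|---|---|
| 6.3, W13 | 1.00 (6.7%) | 0.90 (8.0%) | 0.80 (16.1%) |
| 6.3, W25 | 1.00 (4.9%) | 0.87 (8.5%) | 0.74 (20.2%) |
| 6.3, W45 | 1.01 (5.3%) | 0.82 (8.2%) | 0.69 (20.5%) |
| 11.5, W13 | 1.02 (5.3%) | 0.94 (5.0%) | 0.87 (9.9%) |
| 11.5, W25 | 0.98 (6.0%) | 0.88 (6.8%) | 0.79 (14.4%) |
| 11.5, W45 | 0.99 (5.1%) | 0.86 (8.4%) | 0.71 (19.0%) |

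Restricting to patients progression-free at the visit gives HRs of 0.98 to 1.03 and rejection of 1.6% to 6.0% across all 18 settings. The lowest rates are at W45 with m = 6.3, where few patients remain.

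**Step 3: dependence on post-progression sampling.** A separate null simulation (N = 20, log-ALC, falls of 20–40%, both medians, 300 runs per setting and so less precise) gave rejection of about 7–35% if all progressors have the later CBC, 4–18% if half do, and 4–11% if a quarter do.

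**Step 4: what the time origin contributes.** Among patients who are all event-free at visit time t, nobody fails before t. Counting from t instead of from treatment start subtracts the same constant from every time and leaves each Cox risk set, and so the HR, unchanged. The restriction removes the bias; moving the clock does not.

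**The case against.** **Post-progression counts are inferred, not certain.** Section 5.8 defers to the calendar, whose follow-up column is survival at 2 and 5 years. CBCs are tied to treatment: W13, W25 and W37 are injection visits, Section 9.9 places W45 eight weeks after the last dose, weekly CBCs are not done specifically for the study, and the CBC form in Section 11 follows standard of care. A reader could conclude that stopped patients move straight to survival follow-up. That reading is possible, and it is why the sampling share in Step 3 matters. But Section 5.8 does not say it, and Section 15.3.5 does not exclude such values. Even on that reading a smaller gap remains. Treatment ends at confirmed progression, while Section 13.2 back-dates the event to the first radiographic evidence, so counts taken between the two dates still follow the PFS event.

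**The clock and OS.** A reader might infer that starting PFS at treatment is itself the flaw, or that the OS models share it. Step 4 answers the first. On the second, anyone with an ALC at a visit is alive then, so an OS landmark changes essentially nothing.

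**The time-varying model.** A reader might think that it too needs repair. In a standard fit a patient leaves the risk set at the event, so it already uses only pre-event ALC for PFS. The plan therefore has one analysis free of this bias, which lessens the concern but leaves the fixed-time fits exposed.

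**The illustrative inputs.** The 6.3 and 11.5 month medians belong to IDH1-wildtype, MGMT-unmethylated glioblastoma, in a cohort whose PFS is "defined from date of surgery to date of progression or death due to disease or date of last clinical follow up". The randomized phase II admits grade III, grade IV and high-risk grade II gliomas whatever their MGMT status. The fall in ALC has no source in the documents. Both objections stand: the shares and rejection rates show what could happen and are not estimates for this trial.

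**Conclusion.** The gap is real and confined to the fixed-time PFS models at visits after W4. As written, the plan allows an ALC measured after progression to act as a predictor of that progression, and the separate time-varying model does not correct those fits.

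The size is uncertain. With 20 patients, the main simulation gives false-positive rates from about 5% (no change in ALC, or a modest fall with longer PFS) to about 20% (a fall of 400 with every surviving progressor sampled). The sampling check reached 35% at its extreme. With no change in ALC after progression there is no bias, and if counts rose instead, the distortion would run the other way.

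Two larger claims are tempting but unsupported. Pooling the 19 phase I patients with the 20 in phase II would raise the rates, but Section 15.2.4 presents phase I descriptively and no pooling is planned. Nor do these models decide the trial's question. The phase II primary objective is ALC by arm, no objective in Section 2 relates ALC to PFS or OS, and no stopping or success rule uses these fits. This is a minor, worthwhile correction to a secondary or exploratory analysis.

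**What to change.** Add to Section 15.3.5: each fixed-time Cox model for PFS includes only patients who are progression-free, by the progression date used for PFS, and in follow-up when that ALC is measured; ALC values dated after progression are not used. PFS may be counted from that visit, as is usual for a landmark analysis. Report the number of patients and events in each model. If Section 15.4.5 is meant to carry these models to the expansion cohort, the same rule applies there.

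The cost is SAP wording and a filter on dates, with no change to visits, conduct or sample size. The price is fewer patients in late-visit models. On the illustrative medians, of 20 patients about 11 to 14 would remain at W25 (20 × 0.545 and 20 × 0.717) and about 7 to 11 at W45 (20 × 0.328 and 20 × 0.543), so the latest models may be better reported descriptively.

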### **15.4 The expansion cohort**

#### **15.4.1 Study design**

Based on observed survival improvement in currently enrolled patients, we added (in August 2021) an expansion cohort to the experimental arm. For the expansion cohort, a total of N=31 IDH1 wildtype confirmed by immunohistochemistry and MGMT promoter unmethylated eligible patients will be enrolled to receive the study drug rhIL-7-hyFc.

#### **15.4.2 Endpoint**

The primary endpoint for the expansion cohort is progression free survival (PFS) defined from date of surgery to date of progression or death due to disease or date of last clinical follow up. The secondary endpoints include AE and OS.

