# **3 PATIENT ELIGIBILITY CRITERIA**

## **3.1 Inclusion Criteria**

1. WHO grade III, grade IV, and high risk grade II gliomas that require RT and TMZ treatment.
2. Phase 2 Expansion Cohort ONLY: Must be IDH1 wildtype, as defined by negative immunohistochemistry using an R132H-specific antibody, and MGMT promoter unmethylated glioblastoma multiforme (WHO grade IV).
3. Post-operative treatment must have included radiation and TMZ. Prior Gliadel Wafers are allowed. Glucocorticoid therapy is allowed. TTF device is allowed.
4. Adequate organ and marrow function defined as follows:
  - a. Absolute neutrophil count  $\geq 1,000/\text{mcL}$
  - b. Platelets  $\geq 75,000/\text{mcL}$
  - c. Hemoglobin  $\geq 8 \text{ g/dL}$
  - d. Total bilirubin  $\leq 3.0 \times$  institutional upper limit of normal
  - e. AST (SGOT)/ALT (SGPT)  $\leq 3.0 \times$  institutional upper limit of normal
5. ALC  $\geq 600/\text{mcL}$  (required for phase I and randomized phase II only)
6. Karnofsky Performance Status (KPS)  $\geq 60\%$  (i.e. the patient must be able to care for himself/herself with occasional help from others).
7. Able to provide written informed consent (or consent from a legally authorized representative).
8. Women of childbearing potential must have a negative serum pregnancy test prior to study entry (within 14 days). Patients must be willing to be on adequate contraception during treatment as defined in Section 5.5.
9.  $\geq 18$  years of age.

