### 5.2 Agent Administration

Per standard treatment, patients will receive concurrent RT + TMZ followed by adjuvant

TMZ on Days 1-5 of a 28-day cycle for a total of 6 cycles. rhIL-7hyFc / placebo will be given by intramuscular injection starting at the end of RT + TMZ (within 14 days after last day of RT + TMZ). The second injection will be administered 3-5 days after the last dose of cycle 3 TMZ treatment (~week 13 in treatment schema). The third injection will be given 3-5 days after the last dose of cycle 6 TMZ treatment (~week 25 in treatment schema). Note that the second and third injections should be administered once between Day 3 through 5 following the last dose of TMZ to achieve the strongest response (meaning that if TMZ is delayed, the rhIL-7-hyFc/placebo injections will be delayed as well). The fourth injection (last injection in the study) will be given after completion of monthly TMZ (~Week 37 as shown in Treatment Schema). A total of 4 doses of rhIL-7-hyFc injections are planned.

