#### **5.4.2 Dose Limiting Toxicities (DLTs)**

DLT will be defined as  $\geq$  grade 3 AEs that occur within 30 days from the treatment start possibly related to the drug regimen, with severity graded according to the Common Terminology Criteria for Adverse Events (CTCAE) 5.0.

DLT definition will have the following exceptions:

- Grade 3 dermatologic AEs, including injection site reaction, that resolves to Grade  $\leq$  2 in  $\leq$  3 days with supportive care
- transient Grade 3 influenza-like symptoms or pyrexia controlled with medical management
- Grade 3 fatigue that resolves to Grade  $\leq$  2 in  $\leq$  3 days

- Grade 3 neurologic toxicity responding within  $\leq$  7 days to steroids, anticonvulsants, or electrolyte correction
- Grade 3 laboratory abnormalities that are asymptomatic and considered by the investigator not to be clinically significant

The DLT evaluation period is the first 30 days of therapy. The target DLT rate is <33%.

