#### **15.2.2 Endpoint**

The primary endpoint of the phase I is adverse events (AEs), especially dose limiting toxicity (DLT). DLT will be defined as  $\geq$  grade 3 AEs that occur within 30 days from the date when patients receive the 1st dose of rhIL-7-hyFc administration and are concluded to be possibly, likely or definitely related to the drug regimen that occurs during cycle 1, with severity graded according to the Common Terminology Criteria for Adverse Events (CTCAE) 5.0. Grade 3 dermatologic AEs, including injection site reaction, that resolves to Grade  $\leq 2$  in  $\leq 3$  days with supportive care; transient Grade 3 influenza-like symptoms or pyrexia controlled with medical management; Grade 3 fatigue that resolves to Grade  $\leq 2$  in  $\leq 3$  days; Grade 3 neurologic toxicity responding within  $\leq 7$  days to steroids, anticonvulsants, or electrolyte correction; or Grade 3 laboratory abnormalities that are asymptomatic and considered by the investigator not to be clinically significant will be excluded from the DLT definition.

The secondary endpoint is absolute lymphocyte count (ALC).

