#### **15.4.5 Statistical Analysis**

PFS will be analyzed by the KM method and median PFS will be estimated with 95% CI and tested against the null median PFS of 6.3 months by 2-sided one-sample log rank test. OS will be analyzed similarly. Other endpoints will be analyzed similarly as in Section 15.3.5 but without between arm comparison.

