### **15.5 Analysis set**

The safety analysis set include all patients who have received any dose of the rhIL-7-hyFc.

The efficacy analysis set for the randomized phase II portion of the study includes all patients who have received a dose of rhIL-7-hyFc, completes CBC at baseline and at ~4 weeks prior to adjuvant TMZ, and have evaluable ALC measurements from the CBC labs. The primary analyses will focus on the intent to treat (ITT) patients regardless what treatment they actually receive.

The PFS evaluable patients include patients who received at least one dose of rhIL-7-hyFc.

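### Expansion-cohort PFS is defined two ways, and its surgery clock is not shown to match the 6.3-month null or the dosed-only analysis set

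*Combined protocol and SAP*

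**What the plan says.** Two sections define PFS.

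- Section 15.4.2, written for the expansion cohort, gives "progression free survival (PFS) defined from date of surgery to date of progression" and counts death only when it is due to the disease.
- Section 13.4.6, with no limit to any cohort, says "PFS is defined as the duration of time from start of treatment to time of progression or death, whichever occurs first". It does not say which treatment. The first rhIL-7-hyFc dose is the likelier meaning. For dose-limiting toxicity, Section 5.4.2 counts "AEs that occur within 30 days from the treatment start possibly related to the drug regimen", and Section 15.2.2 expresses the same window as "AEs that occur within 30 days from the date when patients receive the" first dose.

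No rule says which definition prevails.

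The analysis set is in Section 15.5: "The PFS evaluable patients include patients who received at least one dose of rhIL-7-hyFc". The first dose comes well after surgery. Section 3.1 requires that "Post-operative treatment must have included radiation and TMZ", and Section 5.2 has the injections "starting at the end of RT + TMZ (within 14 days after last day of RT + TMZ".

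Section 15.4.5 has PFS "tested against the null median PFS of 6.3 months by 2-sided one-sample log rank test". Section 15.4.3 takes 6.3 months from a published trial and sets it against 11.5 months. Section 1.8.2 reports historical medians of 5.4 and 7.3 months and a phase I median of 11.53 months. None of these figures comes with a time origin or a statement of how far through treatment the patients had to get. No delayed entry or landmark is described.

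**The concern.** With no concurrent control, the comparison means something only if the observed times and the historical median start at the same moment and come from patients selected in the same way.

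On the surgery clock, every analysed patient has a stretch between surgery and first dose in which he or she cannot have died. A one-sample log-rank test without delayed entry still charges the null hazard over that stretch. If the 6.3 months does not carry the same guarantee, expected events can exceed observed events even when the drug does nothing. If it does carry the same guarantee, there is no such gain, and moving the clock to first dose while keeping 6.3 months would penalise the drug.

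The two definitions also count different events. Under Section 13.4.6 a death from another cause is an event; under Section 15.4.2 it is not. The plan does not say which convention the historical figure used.

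**Working it through.** **Inputs from Section 15.4.3.** N = 31; two-sided 5%; medians 6.3 (null) and 11.5 months; exponential PFS; 18 months of accrual plus 12 of follow-up. **Assumed, because the documents do not give them:** the lead L from surgery to first dose (1 to 3 months shown) and the share of pre-dose events kept out of the cohort (0 to 100% shown).

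**1. The plan's own figures.**
- λ0 = ln2/6.3 = 0.1100 and λ1 = ln2/11.5 = 0.0603 per month; hazard ratio 6.3/11.5 = 0.548, as stated.
- Event probability = 1 − [exp(−12λ1) − exp(−30λ1)]/(18λ1) = 1 − (0.4852 − 0.1639)/1.0849 = 0.704 (stated 0.7039).
- Events = 31 × 0.7039 = 21.8 (stated 22).
- Power is 80.0 to 81.4% by three closed-form approximations and 82.4 to 82.7% by simulation of Z = (O − E)/√E with |Z| > 1.96, against 81.05% stated.

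The design arithmetic holds, provided that data, null and alternative share one clock.

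**2. What the lead adds.** Under the null, the same event formula with λ0 gives 0.8838, so 31 × 0.8838 = 27.4 expected events. Each event-free month before first dose adds 31 × 0.1100 = 3.4 expected events and no observed ones. Expected events become 30.8, 34.2 and 37.6 at L = 1, 2 and 3, while about 27.4 are observed on average.

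**3. False finding of benefit, inert drug, surgery clock, no delayed entry.** Here 6.3 months is counted from surgery in unselected patients. The chance of an event before first dose is 1 − exp(−λ0L) = 10.4, 19.8 and 28.1% at L = 1, 2 and 3. A share of those events is removed; the rest stay in with their true dates. Simulated favourable tail:

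| Pre-dose events kept out | L = 1 | L = 2 | L = 3 |
|---|---|---|---|
| 0% | 1.8% | 1.7% | 1.7% |
| 25% | 2.3% | 2.9% | 3.7% |
| 50% | 3.2% | 5.3% | 7.9% |
| 75% | 4.2% | 9.2% | 16.3% |
| 100% | 5.9% | 15.7% | 33.6% |

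Repeat runs differ by about 0.3 of a point or less. The matched design gives 1.7%. The bottom row also applies if 6.3 months was counted from first dose and no analysed patient had an earlier event.

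**4. Delayed entry.** Charging the null only from first dose, in the bottom-row setting, returns the tail to 1.7 to 1.8% at every L.

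**5. Null from surgery in similarly selected patients** (median 6.3 − L after first dose). On the surgery clock the false-benefit tail is 0.5% (L = 1) and 0.07% (L = 2), so there is no inflation. On a first-dose clock with 6.3 kept, an inert drug would look significantly worse in 18% (L = 1) or 57% (L = 2) of trials. With an unselected, exponential historical group, that tail stays at its ordinary 3.6%.

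**6. Power, with 11.5 months counted from surgery** (median 11.5 − L after first dose). On the surgery clock it is about 85 to 86.5% for L = 1 to 3. On a first-dose clock against an unchanged 6.3 it is about 70, 52 and 41% at L = 1, 2 and 2.5. The latter figures arise only if the clock is moved.

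**7. The median.** For an inert drug with a median of 6.3 months after first dose, the Kaplan–Meier median from surgery is 8.2 months at a fixed 2-month lead, with or without delayed entry. With leads spread uniformly over 1 to 3 months it is 8.3 without and 7.4 with delayed entry. Neither is 6.3, so delayed entry repairs the test but not the median.

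**The case against.** Section 15.4.2 is the cohort's own definition of its primary endpoint and is clear about surgery. Section 13.4.6 is general, and PFS is also an exploratory objective in the other two parts of the study. On the usual rule that the specific text governs, the clock is surgery. This stands: the conflict needs a wording repair, but it does not leave the cohort's clock wide open.

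The null comes from a cited publication. Not repeating its time origin is a gap in reporting, not evidence of a mismatch. This stands too.

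A reader might infer that the test leans toward benefit unless the historical patients were selected in the same way. The documents do not support that. With an unselected null counted from surgery and no pre-dose events screened out, the false-benefit rate is about 1.7%, the matched value. The dosed-only set necessarily removes only deaths before first dose; Sections 3.1 and 3.2 do not exclude earlier progression. The 6, 16 and 34% figures therefore need every pre-dose event removed, or a null counted from first dose, and they rest on an assumed lead.

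A reader might also infer that the sample size is wrong. It is not shown to be: the power reproduces, and the losses in step 6 need a first-dose clock that Section 15.4.2 does not specify.

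What the objection does not answer is that settling the clock at surgery leaves that clock on a dosed-only set, with no delayed entry, against a null of unstated origin. Nor does it answer the difference in which deaths count.

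**Conclusion.** The point holds as an unmatched comparison on a primary endpoint, not as a demonstrated bias. Two definitions of PFS differ in origin and in event. The one that most naturally governs puts time during which no analysed patient could have died under the null hazard.

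For an inert drug and an assumed lead of 1 to 3 months, false benefit is about 1.7% if no pre-dose events are kept out, 2 to 4% if a quarter are, 3 to 8% if half are, and at most 6, 16 and 34% if all are. If 6.3 months was counted from surgery in similarly selected patients there is no inflation. These figures rest on exponential PFS and on leads and screening shares that the documents do not give, so neither direction nor size is established. It should be fixed before the primary analysis, because the plan does not let a reader tell which case applies.

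**What to change.** 1. Use one time zero and one event definition in Sections 13.4.6 and 15.4.2, and say whether deaths from other causes count.
2. Choose one of two routes. (a) Count PFS from first rhIL-7-hyFc dose, with null and alternative put on that origin. (b) Keep surgery, with delayed entry at first dose in both the Kaplan–Meier estimate and the expected-event count, and a null hazard valid on that clock. Under (b), label the median as conditional on being event-free at first dose and do not set it beside 6.3 months.
3. State the time origin and population of the 6.3 and 11.5 months. Do not move the clock while keeping 6.3 unchecked.
4. State how progression dated before first dose is handled, since Section 13.2 back-dates confirmed progression to its first radiographic sign.
5. Restate power if the clock or either median changes.

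The cost is wording, a check of the historical source, and a check of how the phase I PFS was computed. If the surgery clock stays, surgery and first-dose dates are both needed; Section 11 lists forms rather than fields, so the documents do not show whether both are captured. The reported median or the power may come out less favourable.
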